**Clinical Observation Of The Gynecological
Iron-Deficiency Anemia Treated With
Buxue Yimu Pills**

Version 2 (June,2017)

CONTENTS

A. OBJECT

B. STUDY METHOD AND DESIGN

C. TECHNICAL ROUTE

D. STATISTICS ANALYSIS

E. QUALITY CONTROL MEASUREMENT AND RESULT

PUBLICATION

F. SOURCE(S) OF FUNDING

A. OBJECT

Buxue Yimu Pills, Ferrous Sulfate each improve anemia, but they do so by different mechanisms. We generally treat patients with uncomplicated Iron Deficiency Anemia with oral iron due to the ease of administration, and Ferrous Sulfate is one of the most commonly used drugs.

Buxue Yimu Pills consists of multiple Chinese herbs including Angelica Sinensis, Astragalus, Donkey-Hide Gelatin, Herba Leonuri, Citrus etc., which gains widespread application in the treatment after women's abortion or operations of uterine cavity.

This study evaluates Buxue Yimu Pills, Ferrous Sulfate and the addition of Buxue Yimu Pills to Ferrous Sulfate in the treatment of Iron-Deficiency Anemia in adult women, with the object to perform clinical efficacy and safety assessment. In addition, we expect to conduct research on its pharmacodynamics, trying to probe into the mechanism and pharmacodynamic material basis of this mysterious traditional Chinese medicine.

B. STUDY DESIGN AND METHOD

— **STUDY DESIGN:** 180 women with mild to moderate Iron Deficiency Anemia were observed in a prospective multi-center randomized controlled clinical trial.

Inclusion Criteria:

1. Subject is a female between the age of 18 and 50.
2. Subject suffers from mild to moderate anemia with a hemoglobin between 80g/L and 110 g/L.
3. Subject has definite gynecological etiological factors of iron deficiency
4. Subject provides written informed consent.

Exclusion Criteria:

1. Subject underwent chronic digestive tract inflammation, uncontrolled digestive or urinary system bleeding.
2. Subject has other complications in addition to gynecological diseases leading to iron deficiency, such as hemorrhagic diseases of hematologic system, parasitic diseases like ancylostomiasis, chronic intravascular hemolysis, mechanical hemolysis like prosthetic valve, renal dysfunction and hemodialysis.
3. Subject is pregnant or lactating.
4. Subject has a severe systemic disease, such as cardiovascular system
5. Subject has a history of malignancy or radiotherapy.
6. Subject has undergone any Iron deficiency anemia treatment including Iron supplements or blood transfusion within 1 month prior to randomization.

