7. Subject has mental disorder incapable of elementary cooperations.
8. Subject has participated in other clinical researches of medicine within 1 month prior to randomization.

—**METHODS:** The participants were divided randomly into 3 groups:

- a. Experimental group1(60 patients): Buxue Yimu Pills 12g pill by mouth, twice daily.
- b. Experimental group2(60 patients): Buxue Yimu Pills 12g pill by mouth, twice daily and Ferrous Sulfate 0.3g tablet by mouth, three times daily.
- c. Active Comparator group (60 patients): Ferrous Sulfate 0.3g tablet by mouth, three times daily.

—**TREATMENT PERIOD:** 1month.

—**OUTCOMES MEASUREMENT :**

Primary Outcome (Anemia Related Assessment, Clinical Efficacy Assessment): Complete Blood Count, Urine Routine, Reticulocyte Count, Iron Metabolism index (Serum Iron, Total Iron Binding Capacity, Serum Ferritin), Coagulation Indexes (Activated Partial Thromboplastin Time, APTT), Prothrombin Time (PT), Fibrinogen (FIB), Thrombin Time(TT), The Short Form-36 Health Survey (Sf-36).

Secondary Outcome (Safety Assessment): Hepatic Function, Renal Function, Blood Glucose, Electrolyte Semiconductor Junction, Electrocardiogram(ECG)

Other Pre-Specified Outcome (Metabonomics Assessment): Build up a new therapeutic evaluation system about Buxue Yimu Pills in the treatment of Gynecological Iron-Deficiency Anemia, which integrating clinical information with metabonomics, to probe into the mechanism and pharmacodynamic material basis of this mysterious traditional Chinese medicine.

C. TECHNICAL ROUTE

Screening Period (Day -30~0)

1. We enrolled in-patients according to the uniform inclusion/ exclusion criteria above, and informed consent will be signed by all study participants before joining in the study.
2. Collect medical history and certain demographic features of every participant, and perform general physical examination as well as gynecologic physical examination.
3. Complete outcomes measurement above.
4. Make the appointment for the follow-up.

The First Follow-Up Period (Day -30~0)

1. Group randomly and distribute medicine and patient diary pamphlet.
2. Inform application notice.
3. Make the appointment for the next follow-up.

The Second Follow-Up Period(Day0~30)

1. Collect medical history and certain demographic features of every participant, and perform general physical examination as well as gynecologic physical examination, again.
2. Complete outcomes re-measurement above.

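### SF-36, a self-reported score, is a primary efficacy outcome although no masking is described, so a difference in expectation between arms could alone give a significant primary result

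*Combined protocol and SAP*

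**What the plan says.** In section B, under outcomes measurement, the list headed "Primary Outcome (Anemia Related Assessment, Clinical Efficacy Assessment" consists of blood, urine, iron and coagulation measures and ends with "The Short Form-36 Health Survey (Sf-36". No item in the list is marked as leading or supporting, and no SF-36 scale or summary score is named.

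The methods paragraph of section B defines the arms:

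- "Experimental group1(60 patients): Buxue Yimu Pills 12g pill by mouth, twice daily"
- Experimental group 2, also 60 women: "Buxue Yimu Pills 12g pill by mouth, twice daily and Ferrous Sulfate 0.3g tablet by mouth, three times daily"
- "Active Comparator group (60 patients): Ferrous Sulfate 0.3g tablet by mouth, three times daily"

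The design is described as a "prospective multi-center randomized controlled clinical trial". Blinding, masking, placebo and open label are not mentioned anywhere in the document. In section C the allocation step reads "Group randomly and distribute medicine and patient diary pamphlet", with nothing on concealing what is handed out. All outcomes are measured at screening, before that step, and again at the Day 0 to 30 visit.

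Section D specifies unpaired t-tests or chi-square tests and calls any p-value below 0.05 significant. It does not distinguish between outcomes.

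**The concern.** A woman given only pills, only tablets, or both can tell her regimen from what she takes and how often. SF-36 records how she rates her own health, so her view of the treatment can enter the score directly. That route is far weaker for hemoglobin or ferritin. The plan nevertheless gives both kinds of measure the same primary standing and the same significance rule.

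At stake is a false efficacy claim. If the arms differ in expectation, the SF-36 comparison is shifted even when the drugs do equally well, and the plan would allow that shift to be reported as a significant primary result.

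This is a different problem from the length of the primary list. A multiplicity correction limits chance findings, but it does not remove a systematic shift.

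**Working it through.** The plan contains no power calculation and no SF-36 standard deviation, effect size or bias figure, so there is no stated number to reproduce. The check asks how large an expectation difference would have to be to matter.

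**Inputs from the documents:** 60 women per arm (section B); unpaired t-test and significance threshold 0.05 (section D).

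**Assumptions:** the test is two-sided (section D does not say); there is no true drug effect; all 60 per arm are analysed; the SF-36 score is roughly normal with a common SD; knowledge of treatment shifts the mean difference between two arms by b SD, with b = 0.1, 0.2 or 0.3.

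**Step 1. Difference needed for significance.** Degrees of freedom are 2 × 60 − 2 = 118 and the critical t is 1.980. The observed difference must reach 1.980 × √(2/60) = 1.980 × 0.1826 = 0.36 SD.

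**Step 2. Chance of reaching it by bias alone.** Under a shift of b SD the t statistic is non-central t with 118 degrees of freedom and non-centrality b × √(60/2) = 5.477b. The rejection probability is P(t > 1.980) + P(t < −1.980).

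| Assumed bias b (SD) | Non-centrality | In the direction of the bias | Opposite direction | Total |
|---|---|---|---|---|
| 0 | 0 | 0.025 | 0.025 | 5.0% |
| 0.1 | 0.548 | 0.078 | 0.006 | 8.4% |
| 0.2 | 1.095 | 0.191 | 0.001 | 19.2% |
| 0.3 | 1.643 | 0.371 | 0.000 | 37.1% |

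The totals are the same whichever arm the bias favours.

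**Step 3. Sensitivity to sample size.** With 51 per arm (an assumed 15% loss: 60 × 0.85 = 51), the totals for 0.1, 0.2 and 0.3 SD are 7.9%, 17.0% and 32.3%. With 120 per arm, a bias of 0.2 SD gives 33.9%. Adding patients makes the problem worse, because the test becomes better at detecting the bias.

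These are figures for one SF-36 score in one pairwise comparison. The plan does not say which score, or which of the three pairwise comparisons, would be tested.

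**The case against.** The strongest objections are these.

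- **The document never says the trial is unmasked.** This is correct. Knowledge of treatment is inferred from the listed regimens and from the absence of any dummy product or masking step. The inference is strong, but it should be worded as one.
- **All arms receive an active product, so only a difference in expectation matters.** This also stands. A reader might infer that the bias favours the combination or the herbal arms. The documents do not support that. Section A says that both products improve anemia and describes ferrous sulfate as among the most commonly used drugs, so expectation could favour iron or be about even. Taking two products on two schedules could also lower self-rated health.
- **Nothing in the plan anchors 0.1 to 0.3 SD.** True. The table shows what a modest bias could do, not that one is likely. At 0.1 SD the rise is small.
- **Baseline SF-36 is collected before allocation.** This is a real merit, but it protects only the baseline score. The follow-up score remains exposed.
- **Naming a single primary endpoint to solve the multiplicity problem would remove SF-36 from the list anyway.** The remedies do overlap. The multiplicity argument alone, however, would not stop a sponsor from choosing SF-36 as that endpoint or from resting a claim on it as a secondary.
- **Patient-reported health is a legitimate part of an efficacy assessment.** Agreed. The issue is its primary standing without masking, not its collection.

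A reader might also infer that women learn their blood results before answering, and ask for a fixed order at the visit. The plan sets no order, and a fixed order would not address knowledge of treatment.

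**Conclusion.** The concern holds in a limited form. SF-36 is a primary efficacy outcome, masking is not described and is improbable given the regimens, and no rule keeps SF-36 from carrying a primary claim alone. An expectation difference in either direction could therefore yield a significant primary result without a drug effect. The probability per comparison is 8%, 19% or 37% instead of 5% if the bias is 0.1, 0.2 or 0.3 SD. That range is an assumption, and the calculation also assumes 60 analysed per arm and a two-sided test.

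The documents do not establish that the trial is open label, that such a bias will occur, or which arm it would favour. The point is confined to SF-36 and does not undermine the laboratory outcomes. It should be changed because the change is cheap.

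**What to change.** In sections B and D:

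1. Move SF-36 from the primary list to a supportive secondary outcome, and name the scale or summary score to be analysed.
2. State that the treatments are not masked or, if masking exists, describe it.
3. State that no efficacy claim may rest on SF-36 alone.
4. Rest the primary claim on hemoglobin. It comes from the blood count already collected at both time points, and section B already uses it to define eligibility.

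The cost is a few sentences of wording. No placebo, extra patients, extra measurements or change of treatment is needed. The one real loss is that the sponsor gives up a primary quality-of-life claim. If the primary list is also shortened for multiplicity reasons, items 1 and 4 can be made in the same edit; items 2 and 3 are still needed.

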3. Take back the medicine and patient diary pamphlet.

D. STATISTICS ANALYSIS

Data was analyzed using SPSS Version 18. All quantitative informations are expressed as mean values \pm standard deviation (SD). Statistical significance was assessed using unpaired Student's t-test or chi-square test. Probability values of less than 0.05 were considered significant and an asterisk identifies such significance in the figures. We will also compare the adverse effect of each group using descriptive statistics.

E. QUALITY CONTROL MEASUREMENT AND RESULT PUBLICATION

1. Every center of the research possesses the competence of scientific research to conduct clinical studies. Special people from each center will be put in charge of the research and monitoring the whole procedure. The rights and interests, responsibility and obligation of all centers will be standardized with the research agreement.
2. The maintenance, secrecy and safety of data and informations will be guaranteed by Department of Obstetrics and Gynecology, Peking Union Medical College Hospital.
3. Every center is responsible to subject enrollment and finish the prospective follow up.
4. The researchers' findings will be released in a paper published online.

F. SOURCE(S) OF FUNDING

1. This study does not charge any fee to any patients.
2. All the investigational drugs and cost of the study are provided by Qian Jin Pharmaceutical CO., LTD.

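### The metabonomics outcome falls under an unadjusted P<0.05 rule with no multiplicity control or validation, so chance metabolites, and possibly inflated accuracy, could be reported as findings

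*Combined protocol and SAP*

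**What the plan says.** The metabonomics outcome is a single sentence in Section B, under the Other Pre-Specified Outcome. It promises to "Build up a new therapeutic evaluation system about Buxue Yimu Pills in the treatment of Gynecological Iron-Deficiency Anemia", by "integrating clinical information with metabonomics", so as to explore how the pills work and which constituents are responsible. Section A states the same exploratory aim. No sample type, assay platform, number of metabolites, target variable, model or accuracy measure is given.

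Section D is the whole analysis plan. Its inferential content is "Statistical significance was assessed using unpaired Student's t-test or chi-square test" and "Probability values of less than 0.05 were considered significant and an asterisk identifies such significance in the figures". It gives metabonomics no rule of its own. It mentions no multiplicity adjustment, hold-out set, cross-validation, permutation test or outside cohort.

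The only study population is in Section B: "180 women with mild to moderate Iron Deficiency Anemia were observed", in three arms of 60 (pills alone, pills plus ferrous sulfate, ferrous sulfate alone).

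**The concern.** There are three separate difficulties.

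- **Lists of metabolites.** A per-test 5% rule applied to many metabolites produces false positives in proportion to their number. The plan would mark each with an asterisk, like a real finding.
- **The evaluation system.** A score built from metabolites selected for differing between groups will separate those same groups even if none of the metabolites carries information. A t-test on the score in the same women cannot reveal this. Nothing in the plan prevents performance from being reported that way.
- **Attribution.** Pills alone and ferrous sulfate alone differ in two treatments. A metabolite difference between those arms cannot be credited to the pills as such. The plan does not say which contrast would support a statement about mechanism.

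At stake is the credibility of a declared product of the trial: the metabolite list, any accuracy quoted for the system, and any mechanism drawn from them.

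**Working it through.** **Inputs from the documents.** Arms of 60, and 3 × 60 = 180, which agrees with the stated total. Significance level 0.05 per test. The plan gives no figure for metabolites or for accuracy, so there is nothing further to reproduce.

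**Assumptions.** The number of metabolites p is not stated, so a range of 10 to 1000 is shown. Tests are taken as two-sided because sidedness is not stated. The target is taken as treatment arm, 60 v 60, because the plan names none.

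**Step 1: false flags with no true signal, per two-arm contrast.** The expected number is 0.05 × p. For independent metabolites the chance of at least one is 1 − 0.95^p. For example, at p=50: 0.05 × 50 = 2.5 flags, and 1 − 0.95^50 = 0.923.

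**Step 2: a score built from the flagged metabolites.** Null data were simulated for 60 v 60 women, with 500 replicates up to p=200 and 300 above. Metabolites with P<0.05 were kept and their signed z-scores summed. The AUC was then computed in the same women, in new women, and by 5-fold cross-validation with selection repeated in each fold. Means are over replicates in which at least one metabolite was selected.

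| p | Expected false flags | Chance of ≥1 | AUC, same women | Correctly classified, same women | AUC, new women | AUC, cross-validated |
|---|---|---|---|---|---|---|
| 10 | 0.5 | 40.1% | 0.63 | 59% | 0.50 | 0.52 |
| 20 | 1 | 64.2% | 0.65 | 60% | 0.50 | 0.52 |
| 50 | 2.5 | 92.3% | 0.68 | 63% | 0.50 | 0.50 |
| 100 | 5 | 99.4% | 0.74 | 68% | 0.50 | 0.50 |
| 200 | 10 | about 100% | 0.83 | 75% | 0.50 | 0.49 |
| 500 | 25 | about 100% | 0.94 | 86% | 0.50 | 0.50 |
| 1000 | 50 | about 100% | 0.98 | 94% | 0.50 | 0.50 |

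Whenever any metabolite was selected, the resulting score differed between the groups at P<0.05 in the same women in 100% of replicates.

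**Step 3: sensitivity.** With metabolites correlated at r=0.7 in blocks of about 10, the same-women AUC falls to 0.64 (p=50), 0.72 (p=200) and 0.81 (p=500). With 30 v 30, as might arise for responders against non-responders within one arm, it rises to 0.76, 0.91 and 0.99 at the same three values of p. In new women it stays at about 0.50 throughout.

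**Step 4: effect of a stricter list rule.** Testing each metabolite at 0.05/p brings the simulated chance of any false flag to 4.0% at p=50 and 4.8% at p=200. When nothing is real, every flagged metabolite is false, so false-discovery-rate control at 5% holds the chance of any false flag to the same 5% ceiling for independent features. It is less strict than 0.05/p when some signals are real.

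**Step 5: contrasts.** Group 1 receives pills, group 2 pills plus iron, group 3 iron. Groups 1 and 3 differ in both treatments. Groups 2 and 3 differ only in the pills, given on top of iron.

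**The case against.** The strongest reply is that the plan leaves the method open and does not choose a wrong one. A reader might infer that the system will be built and judged on the same women. The documents do not say so: they name no judging step, and Section D does not tie P<0.05 to building or scoring the system. That objection stands, so the AUC figures are conditional. It does not remove the false-flag problem, because the Section D rule is the only one available for comparing metabolites between arms.

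The size also depends on an unstated p. With 10 or 20 independent candidates, nothing is flagged about 60% or 36% of the time (0.95^10 and 0.95^20), and the apparent AUC is only 0.63 to 0.65 when something is. Correlation between metabolites lowers it further. The simulated target (treatment arm) and score are illustrative choices; a system that evaluates treatment may well be aimed at response instead. All of this stands.

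On contrasts, comparing group 1 with group 3 is legitimate as pills versus iron, and the plan does not say it will be read otherwise. Group 2 v group 3 shows only the effect of adding pills to iron. The remedy is therefore a rule on interpretation, and it does not forbid any comparison.

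A reader might also infer that samples taken on treatment contain compounds from the pills that separate the arms trivially. The documents give no sample type, assay or time since last dose, so this cannot be asserted. Excluding such compounds could also cut against the stated interest in the active constituents.

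**Conclusion.** The concern holds in a limited form. For the metabonomics outcome the plan's only rule is an unadjusted P<0.05. With no true signal it flags about 0.05 × p metabolites per two-arm contrast. This follows from the rule as written; only p and, for the chance of at least one flag, independence are assumed.

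The inflation of apparent accuracy is a risk that the plan leaves open, and the documents do not state it as a planned step. If it occurred, it would range from modest at 10 to 20 metabolites to severe at several hundred, against a true AUC of 0.50.

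The outcome is exploratory, and the primary comparisons between arms are not affected. The change is still worth making, because a better rule is available and needs no new patients or samples.

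**What to change.** Add to Section D, for the metabonomics outcome:

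1. Metabolite lists are controlled at a 5% false discovery rate in place of P<0.05.
2. The performance of any evaluation system is reported only from cross-validation with all feature selection inside the folds, together with a permutation test that repeats the whole procedure. The target variable must be named for this to be carried out. Ordinary k-fold splitting is enough; the number of centers is not given, so leaving out one center at a time cannot be assumed workable.
3. A metabolite difference between group 1 and group 3 is described as pills versus iron. A difference is attributed to adding the pills only from group 2 versus group 3.

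The cost is analysis wording and some computing time. The downside is fewer metabolites called significant and lower reported accuracy.

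### The safety laboratory results are planned only as mean ± SD, with no abnormality criterion, count, shift table or listing, so one or two women with grossly abnormal values would not be visible in the planned summary

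*Combined protocol and SAP*

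**What the plan says.** Section A makes safety assessment part of the trial's object. Section B defines that assessment as "Secondary Outcome (Safety Assessment): Hepatic Function, Renal Function, Blood Glucose", followed by electrolytes and ECG, so it is mostly numeric. Section C has these measured at screening and once more at the second follow-up, in the Day 0 to 30 period.

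Section D is the whole analysis plan. On display it says "All quantitative informations are expressed as mean values" ± SD, with no exception for safety data. On testing it says "Statistical significance was assessed using unpaired Student's t-test or chi-square test" and "Probability values of less than 0.05 were considered significant". It does not say which test belongs to which outcome. Its one further safety provision is "We will also compare the adverse effect of each group using descriptive statistics". It does not define an adverse effect or say whether an abnormal laboratory value counts as one.

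Neither Section B nor Section D gives a reference limit, a grade, a shift table, a count of abnormal results or a listing of individual women.

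**The concern.** Liver or kidney toxicity typically appears as large changes in a few people, not as a modest shift of a whole arm. A mean ± SD averages those few into the rest. A t-test on the means does not recover them, because an extreme value raises the SD along with the mean. If the laboratory results are reported only in the form Section D prescribes, a reader may see no asterisk and take that as reassurance about a multi-herb product, without learning whether any woman had a grossly abnormal result.

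**Working it through.** The plan gives no power, SD or threshold for any safety variable, so it has no figure of its own to reproduce.

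**Inputs from the documents.** There are 60 women in each arm (Section B: "Experimental group1(60 patients", "Experimental group2(60 patients", "Active Comparator group (60 patients") and significance is at 0.05 (Section D). Sidedness is not stated; I take it as two-sided. For two arms of 60 there are 118 degrees of freedom and the critical t is 1.980.

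**Step 1: result that needs only n.** Let k of n women in one arm share a value D above everyone else, and let D dominate the ordinary spread.
- Difference in means: kD/n.
- Variance in the affected arm: D²k(n−k)/[n(n−1)]. The other arm contributes essentially nothing.
- Standard error of the difference: the square root of that variance divided by n.
- D cancels, leaving t = √[k(n−1)/(n−k)].

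With n = 60:

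| k | t | p |
|---|---|---|
| 1 | √(59/59) = 1.00 | 0.32 |
| 2 | √(118/58) = 1.43 | 0.16 |
| 3 | √(177/57) = 1.76 | 0.08 |
| 4 | √(236/56) = 2.05 | 0.042 |

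One or two women, however extreme, cannot reach 1.98 by themselves. About four are needed.

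**Step 2: what mean ± SD shows.** Assume a liver enzyme with mean 20 and SD 8, and put one woman at 200. The arm mean becomes (59 × 20 + 200)/60 = 23. The SD becomes about √[(58 × 64 + 180² × 59/60)/59] = √603, or about 24.5. The SD is odd, but it does not say whether one woman or several caused it, how high she was, or whether she was normal at screening.

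**Step 3: simulated chance of P<0.05.** The documents give no ALT distribution. Assume lognormal values with median 18 U/L and log-SD 0.4, 60 per arm, a pooled t-test, and k women in one arm replaced by high values. With no such woman the rate is 5%.
- One woman: about 1% if her value lies in 120–300, rising to about 4% in 80–120.
- Two women: 2.2% in 120–300, 6.3% in 120–160, 7.4% near 120, and a little over 8% in 80–120.

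The rate falls as the values become more extreme, because the SD inflates.

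**Step 4: would a test on counts do better?**
- 1/60 against 0/60: uncorrected chi-square p = 0.32, Fisher p = 1.00.
- 2/60 against 0/60: chi-square p = 0.15, Fisher p = 0.50.
- 4/60 against 0/60: chi-square p = 0.042, Fisher p = 0.12.

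No test flags one or two of 60.

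**Step 5: what counts with intervals show.** For 2/60 the exact 95% interval is 0.4% to 11.5%. For 0/60 the one-sided 95% upper bound is 1 − 0.05^(1/60) = 4.9%. Both show how much remains unknown, which a non-significant t-test does not.

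**The case against.** The strongest reply is that Section D contains a second safety route. Adverse effects are to be compared descriptively by group, diaries are collected, and history and examination are repeated at the end visit. A woman with a grossly abnormal liver test could be reported there. That stands: a reader might infer that such cases would go unreported, or would inevitably be written up as no significant difference, and the documents do not support either. But with no laboratory criterion tied to that sentence, whether a result is captured is left to each center.

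Second, a reader might infer that the plan prescribes a t-test for the safety laboratory values. It does not. The t-test is merely the only named test that compares means. A chi-square test on normal or abnormal status is not excluded, and ECG lends itself to that. However, no cut-off is given. The mean ± SD rule, by contrast, is explicit. Section D does not forbid additional counts or listings, but it plans none.

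Third, it is tempting to say that two severe cases push the chance of significance below 5%, or that the t-test is the wrong test and another would find them. The first holds for some assumed ranges and fails for others (Step 3). The second is contradicted by Step 4: the limit is rare events in 60 women per arm, whichever test is used.

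**Conclusion.** The concern holds as a gap in the planned reporting. The only summary specified for the numeric safety outcomes hides individual abnormal results, and nothing else in the plan is specified to show them. The limiting t values of 1.00 and 1.43 for one and two women rest only on 60 per arm and a two-sided 0.05 test; dropout would change n slightly and not the conclusion. The simulated rates, about 1–4% with one woman and 2–8% with two against 5% under the null, depend on the assumed ALT distribution and on how extreme the values are. Use them as illustration. This should be corrected because safety is a stated object of the trial, but it does not affect the design or data collection.

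**What to change.** In Section D, add for each safety laboratory test and for ECG, by arm:
- a screening-to-end shift table (low, normal or high against the local reference range; normal or abnormal for ECG);
- the number and percentage of women normal at screening and abnormal at the end, with exact 95% confidence intervals;
- a listing of those women with both values.

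Keep mean ± SD as a supplement. State that a non-significant difference will not be read as evidence of safety. Do not substitute another significance test.

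The cost is a paragraph of SAP text and a few tables. Both measurements are already planned, so no new samples are needed, but each site must supply its laboratory reference ranges. If only one item can be added, the normal-to-abnormal counts by arm close most of the gap.

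### Section D names only an unpaired t-test for quantitative outcomes, so the pre-randomization baseline goes unused and the choice between end value and change is left open

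*Combined protocol and SAP*

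**What the plan says.** Section D is the whole analysis plan. Its one inferential sentence is "Statistical significance was assessed using unpaired Student's t-test or chi-square test", with significance at 0.05. On summaries it says "All quantitative informations are expressed as mean values" with standard deviations, without saying values of what. It names no covariate, no model and no contrast between groups. Section B lists outcomes by the name of the laboratory test or questionnaire, so it does not define the analysed variable either.

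Section C fixes the order of events. At screening: "Complete outcomes measurement above". At the visit after that: "Group randomly and distribute medicine and patient diary pamphlet". At the second follow-up: "Complete outcomes re-measurement above". Each listed outcome therefore has a planned value before randomization and another at the end of treatment.

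One inclusion criterion bears on how informative the baseline is: "Subject suffers from mild to moderate anemia with a hemoglobin between 80g/L and 110 g/L".

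**The concern.** A baseline measured before randomization on the same scale as the outcome can be used to explain part of the variation in the end value. The plan collects it for every outcome and gives it no role in the analysis. If baseline and end value are well correlated, confidence intervals are wider than they need to be.

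The sentence in section D also fits two different between-arm analyses, one of end values and one of changes from baseline. These can disagree on the same data, and a reader of the eventual report could not tell which was intended.

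The contrast is not stated either. I read the unpaired test as a comparison between arms, its natural use in a randomized trial. Applied to before-versus-after values within an arm, it would ignore the pairing and be the wrong test.

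**Working it through.** **Inputs from the plan.** 180 women in three arms of 60 (section B); significance level 0.05 (section D), taken as two-sided because sidedness is not stated; measurement before randomization and at the end (section C). The plan has no power calculation to reproduce.

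**Assumptions.** Rho, the standard deviations (SDs), the target effect and attrition are not in the documents. I use rho from 0.1 to 0.7, 60 complete patients per arm and a linear baseline-to-end relation. Let k be end SD divided by baseline SD.

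**Step 1: variance per patient, in units of the end-value variance.**
- End value: 1.
- Change: 1 + 1/k² − 2·rho/k.
- ANCOVA: 1 − rho².

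At rho = 0.5, ANCOVA gives 1 − 0.25 = 0.75. The interval is 1 − √0.75 = 13.4% narrower than for end values, and 60 × 0.75 = 45 per arm would match 60 per arm with the end-value t-test.

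**Step 2: power against the end-value t-test.** With noncentrality d·√(60/2) and 118 degrees of freedom, 80% power needs d = 0.516 end-value SDs. ANCOVA power is evaluated at d/√(1 − rho²) with 117 degrees of freedom. This comparison does not depend on k.

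| rho | d/√(1 − rho²) | ANCOVA power | CI narrower by |
|---|---|---|---|
| 0.1 | 0.518 | 80.4% | 0.5% |
| 0.2 | 0.526 | 81.6% | 2.0% |
| 0.3 | 0.541 | 83.6% | 4.6% |
| 0.5 | 0.595 | 89.9% | 13.4% |
| 0.7 | 0.722 | 97.5% | 28.6% |

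**Step 3: the change-score t-test, same d.** The last two columns show how much narrower the ANCOVA interval is than the change-score interval.

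| rho | Power, k = 1 | Power, k = 1.5 | ANCOVA CI narrower, k = 1 | ANCOVA CI narrower, k = 1.5 |
|---|---|---|---|---|
| 0.2 | 60% | 73% | 23% | 10% |
| 0.3 | 66% | 78% | 19% | 7% |
| 0.5 | 80% | 89% | 13% | 2% |
| 0.7 | 95% | 97% | 8% | 0.1% |

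With equal SDs, the end value is more precise than change below rho = 0.5 and less precise above it. So the unstated choice matters even where ANCOVA adds little: at rho = 0.2 with equal SDs, power is 80% on one reading and 60% on the other.

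**Step 4: the open choice.** Treat the two t statistics as bivariate normal with correlation (1 − rho/k)/√(1 + 1/k² − 2·rho/k). Over rho 0.2 to 0.7 and both values of k, exactly one of the two tests is significant in about 15% to 29% of trials at d = 0.516. With no effect, each test keeps 5%, and at least one is significant in about 8% to 9% of trials per outcome and arm pair.

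**Step 5: why ANCOVA closes the choice.** If end = a + t·arm + b·baseline, then end − baseline = a + t·arm + (b − 1)·baseline. The arm difference t is the same whichever variable is modelled.

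**Step 6: error rates.** With equal SDs across arms, simulated type I error of the end-value, change and ANCOVA tests is 4.7% to 5.2%. A single three-arm ANCOVA that pools the residual variance is sensitive to unequal SDs. At rho = 0.3, with no effect and 20,000 simulated trials:
- End SDs 1, 1, 1.5: about 2% for the equal-SD pair and about 7% for the other two pairs.
- End SDs 1, 1.5, 1.5: about 8% for the two wider arms and about 4% for the other pairs.

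Pairwise ANCOVA and the pairwise t-test stay near 5% in both settings. The SD patterns are assumptions.

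**The case against.** The strongest reply is that nothing here is wrong, only possibly inefficient, and the documents cannot show by how much. That largely stands. Rho is not given. For hemoglobin a low value is plausible: entry is limited to 80–110 g/L, and the screening window (Day −30 to 0) and the second follow-up (Day 0 to 30) allow up to about 30 + 30 = 60 days between measurements. At rho of 0.1 to 0.3 the gain over end values is 0 to 4 points of power. The 98% power and 29% narrower interval need rho = 0.7, for which the documents offer no support. Section B also lists ferritin, iron binding capacity, coagulation indexes and SF-36 as primary, and the plan sets no entry range on those; but their rho is unknown too.

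A second reply is that baseline adjustment is not free. That stands for one particular form, the three-arm model with a pooled residual variance (step 6). The arms are three different regimens, so unequal end SDs are possible. It does not stand against ANCOVA fitted to each pair of arms.

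Third, one sentence choosing end value or change would also close the choice. True, but it would leave the baseline information unused.

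A reader might infer more than the documents support:
- *That the planned test is biased or inflates type I error.* As a between-arm test of either variable it does neither. The 8% to 9% arises only if both versions are run and the significant one is reported, and nothing in the plan says so.
- *That the plan uses an unpaired test on paired data.* Section D does not state the contrast, so this is a possibility to exclude by wording, not an error shown.
- *That the trial is underpowered as a result.* There is no stated target effect or SD against which to judge that.

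**Conclusion.** The point holds as one of efficiency and specification. Section D leaves a baseline collected on every outcome unused and does not say which variable is compared, or between which groups. Read as between arms, each pairwise t-test is valid.

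The precision lost against end values runs from almost nothing at rho = 0.1 to intervals 29% wide of the attainable saving at rho = 0.7, that is, ANCOVA intervals 29% narrower. Against change scores it also depends on the SD ratio. These sizes rest on assumed rho and k, 60 complete patients per arm and a reference effect chosen for illustration. For hemoglobin the low end is plausible.

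The case for acting does not need a high rho. Pairwise ANCOVA is not materially worse than either t-test at any rho considered, and it settles end value or change. The change should be made, but the planned test is not invalid without it.

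**What to change.** In section D, for each continuous outcome measured at both visits, replace the unpaired t-test with:

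> For each pair of arms, the end-of-treatment value will be compared by ANCOVA on arm with the baseline value of the same variable as covariate, fitted to the two arms compared (or in one three-arm model with heteroscedasticity-robust standard errors). Adjusted differences will be reported with 95% CIs.

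Do not pool one residual variance over the three arms without robust standard errors. Markedly skewed variables may be log-transformed at both visits; name them in the plan, so that the transformation does not become a new open choice. Categorical results stay with the chi-square test, and adverse effects stay descriptive. Settle the wording before end values are compared by arm.

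The cost is a rewritten paragraph, slightly more analysis work on data already collected and one residual degree of freedom. The pairwise form needs only the standard general linear model in SPSS, the package section D already names. No visit, patient, measurement or allocation changes. Multiplicity across outcomes and arm pairs, and the handling of missing end values, are separate matters that this does not solve.
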